14.10. Interim Analysis

Dose escalation decision will be made as outlined based on available safety and available PK/pharmacodynamic information. No statistical analyses are planned to aid the dose escalation decision.

14.11. Missing Data and Imputation

Missing data generally will not be imputed except those defined in the SAP.

Protocol: LAM-002A-NHL-CLN01

Version 9, 18 Feb 2020

14.12. Protocol Deviations

By-subject listings will be generated for all enrolled subjects' inclusion and exclusion criteria; this includes those subjects who do not meet one or more inclusion criteria, and those subjects who meet one or more exclusion criteria. A list of all protocol deviations will be maintained by the clinical team and will be included in the clinical study report. The impact of the protocol deviation on the efficacy analysis will be evaluated.

Protocol: LAM-002A-NHL-CLN01 Version 9, 18 Feb 2020

15. DIRECT ACESS TO SOURCE DATA/DOCUMENTS

A representative of AI Therapeutics will be allowed to conduct site visits to the investigation facilities for the purpose of monitoring any aspect of the study. The investigator agrees to allow the monitor to inspect the drug storage area, study drug stocks, drug accountability records, subject charts and study source documents, and other records relative to study conduct.

Version 9, 18 Feb 2020

16. STUDY MONITORING

Before an investigational site can enter a subject into the study, a representative of AI Therapeutics will visit the investigational study site to:

- Determine the adequacy of the facilities
- Discuss with the investigator and other personnel their responsibilities with regard to protocol adherence, and the responsibilities of AI Therapeutics or its representatives. This will be documented in a Clinical Study Agreement between AI Therapeutics and the investigator.

During the study, a monitor from AI Therapeutics or its representative will have regular contacts with the investigational site for the following:

- Provide information and support to the investigator
- Confirm that facilities remain acceptable
- Confirm that the investigational team is adhering to the protocol that data are being accurately recorded in the eCRFs, and that investigational product accountability checks are being performed
- Perform source data verification. This includes a comparison of the data in the CRFs with the subject's medical records at the hospital or practice, and other records relevant to the study. This will require direct access to all original records for each subject (e.g., clinic charts)
- Record and report any protocol deviations not previously sent to AI Therapeutics
- Confirm AEs and SAEs have been properly documented on eCRFs, and confirm any SAEs have been forwarded to AI Therapeutics and those SAEs that met criteria for reporting have been forwarded to the IRB

The monitor will be available between visits if the investigator or other staff members need information or advice.

Upon conclusion of the Dose-Escalation (Stage 1) and Expansion (Stage 2) stages of the study, routine site monitoring by AI Therapeutics or its representatives will be discontinued.

16.1. Audits and Inspections

Authorized representatives of AI Therapeutics, a regulatory authority, and/or an IRB may visit the site to perform audits or inspections, including source data verification. The purpose of a AI Therapeutics audit or inspection is to systematically and independently examine all study-related activities and documents to determine whether these activities were conducted, and data were recorded, analyzed, and accurately reported according to the protocol, Good Clinical Practice (GCP) Guidelines of the International Conference on Harmonisation, and any applicable regulatory requirements. The investigator should contact AI Therapeutics immediately if contacted by a regulatory agency about an inspection.

Clinical Study Report AI Therapeutics, Inc. 16.1 Study Information LAM-002A-NHL-CLN01

Protocol: LAM-002A-NHL-CLN01

Version 9, 18 Feb 2020

16.2. Institutional Review Board

The investigator must obtain IRB or Ethics Committee (EC) approval for the investigation. Initial IRB/EC approval, and all materials approved by the IRB/EC for this study, including the subject consent form and recruitment materials, must be maintained by the investigator and made available for inspection.

Version 9, 18 Feb 2020

17. QUALITY CONTROL AND QUALITY ASSURANCE

Qualified staff of AI Therapeutics or its representative will conduct independent monitoring of the clinical study for protocol and GCP compliance periodically.

The investigator will permit direct access of the study monitors and appropriate regulatory authorities to the study data and to the corresponding source data and documents to verify the accuracy of this data.

Version 9, 18 Feb 2020

18. ETHICS

18.1. Ethics Review

The investigator will obtain IRB/EC approval of the clinical protocol and corresponding informed consent form(s); modifications to the clinical protocol and corresponding informed consent forms; and advertisements (i.e., directed at potential research subjects) for study recruitment prior to study implementation. The investigator must submit written approval to AI Therapeutics or designee before enrolling any subject into the study.

The only circumstance in which a deviation from the current IRB/EC approved clinical protocol/consent form(s) may be initiated in the absence of prospective IRB/EC approval is to eliminate an apparent immediate hazard to the research subject(s). In such circumstances, the investigator will promptly notify the IRB/EC of the deviation.

The investigator is also responsible for providing the IRB/EC with reports of any reportable serious adverse drug reactions from any other study conducted with the investigational product. AI Therapeutics will provide this information to the investigator.

Progress reports and notifications of serious adverse drug reactions will be provided to the IRB/EC according to local regulations and guidelines.

18.2. Ethical Conduct of the Study

The clinical research study will be conducted in accordance with the current IRB/EC approved clinical protocol, ICH GCP Guidelines, relevant policies, and requirements of the national regulations and laws.

18.3. Written Informed Consent

The investigator will make certain that an appropriate informed consent process is in place to ensure that potential research subjects, or their authorized representatives, are fully informed about the nature and objectives of the clinical study, the potential risks and benefits of study participation, and their rights as research subjects. The investigator, or a sub-investigator(s) designated by the investigator, will obtain the written, signed informed consent of each subject, or the subject's authorized representative, prior to performing any study-specific procedures on the subject. Subjects must also be notified that they are free to discontinue from the study at any time. The subject (or authorized representative) should be given the opportunity to ask questions and allowed time to consider the information provided. The date and time that the subject or the subject's authorized representative signs the informed consent form and a narrative of the issues discussed during the informed consent process will be documented in the subject's case history. The investigator will retain the original copy of the signed informed consent form, and a copy will be provided to the subject, or to the subject's authorized representative.

The investigator will make certain that appropriate processes and procedures are in place to ensure that ongoing questions and concerns of enrolled subjects are adequately addressed and that subjects are informed of any new information that may affect their decision to continue participation in the clinical study. In the event of substantial changes to the clinical study or the

Clinical Study Report 16.1 Study Information

16.1 Study Information
Protocol: LAM-002A-NHL-CLN01

Version 9, 18 Feb 2020

benefit: risk ratio of study participation, the investigator will obtain the informed consent of enrolled subjects for continued participation in the clinical study.

AI Therapeutics, Inc.

[figure not shown]
LAM-002A-NHL-CLN01

Version 9, 18 Feb 2020

19. DATA COLLECTION, REPORTING AND PROCESSING

The standard flow of the clinical study data from collection to clinical study report is illustrated in Figure 2.

Figure 2: Transmission of Electronic Data

Abbreviations: eCRF = electronic case report form

Data will be transcribed from source into a validated 21 Code of Federal Regulations (CFR) Part 11 compliant, electronic data capture (EDC) system using single data entry. External data will also be imported into the system. Medical Coding (MedDRA and World Health Organization Drug Dictionary [WHODD]) and pharmacokinetic raw and parameter data, for example, will be merged into the database using Statistical Analysis System (SAS) or Excel transfers. Data originators, as well as system administrators, will be trained, authorized, and each assigned an individual identifier (user name and password). Electronic tools (prompts), as well as data review and query, will be used to alert users to and correct for missing data, data inconsistencies, inadmissible values, entries out of range, and to request additional data as applicable. An audit trail will be maintained to record data entries and edits. Data originators will have access to their data during study conduct and will be provided a read-only copy of the final data, audit trail, and queries in a human readable file suitable for long term storage.

The investigator and any vendors will permit study-related monitoring, audits, IRB review, and regulatory inspection(s) by providing direct access to source data/documents. Data entered into the eCRF will be available to the parties responsible for study data management (sponsor, contract research organization [CRO]) as it is entered and can be exported into files compatible with SAS and Excel, among other data formats.

Subject data necessary for analysis and reporting of this study will be transferred via a validated procedure into a validated database or data system (e.g., SAS), to enable the data to be restructured into Industry standards. Clinical data management will be performed in accordance with applicable AI Therapeutics or designee's standards and data cleaning procedures. This is applicable for data recorded on eCRF as well as for data from other sources. Examples of other data would be the medical glossary coding (e.g., AEs, medication) that will be performed with

Version 9, 18 Feb 2020

internationally recognized and accepted dictionaries. Additional details are recorded in the monitoring and data management documentation.

19.1. Inspection of Records

AI Therapeutics will be allowed to conduct site visits to the investigation facilities for the purpose of monitoring any aspect of the study. The investigator agrees to allow the monitor to inspect the drug storage area, study drug stocks, drug accountability records, subject charts and study source documents, and other records relative to study conduct.

19.2. Retention of Records

The investigator will maintain records in accordance with GCP guidelines; to include:

- Food and Drug Administration (FDA) correspondence related to the IND and clinical protocol, including copies of submitted Safety Reports and Annual Reports
- IRB correspondence (including approval notifications) related to the clinical protocol, including copies of AE reports and annual or interim reports
- Current and past versions of the IRB-approved clinical protocol and corresponding IRB-approved consent form(s) and, if applicable, subject recruitment advertisements
- Signed FDA Form 1572 Statement of the investigator
- Financial disclosure information (i.e., for the investigator and for sub-investigators who will be involved in the administration of the study drugs and/or the evaluation of research subjects [i.e., who will contribute significantly to the research study data])
- Curriculum vitae (i.e., for the investigator)
- Certificates of required training, e.g., human subject protections, GCP, and so on (i.e., for the investigator and for all sub-investigators who will be involved in the administration of the study drugs and/or the evaluation of research subjects [i.e., who will contribute significantly to the study data])
- Listing of printed names/signatures. (i.e., for the investigator and for all sub-investigators who will be involved in the administration of the study drugs and/or the evaluation of research subjects [i.e., who will contribute significantly to the study data])
- Normal value(s)/range(s) for medical/laboratory/technical procedures or tests included in the clinical protocol
- Laboratory certification information
- Instructions for on-site preparation and handling of the investigational drug(s), study treatment(s), and other study-related materials (i.e., if not addressed in the clinical protocol)
- Responsibility delegation log
- Signed informed consent forms
- Completed eCRFs, signed and dated by the investigator
- Source Documents or certified copies of Source Documents

Clinical Study Report 16.1 Study Information

Protocol: LAM-002A-NHL-CLN01

Version 9, 18 Feb 2020

- Monitoring visit reports
- Copies of investigator correspondence (including notifications of safety information) to subinvestigators
- Subject screening and enrollment logs
- Subject identification code list
- Investigational drug accountability records, including documentation of drug disposal.
- Final clinical study report.

The investigator must maintain all documentation relating to the study for a period of 2 years after the last marketing application approval or, if not approved, 2 years following the discontinuance of the test article for investigation. If it becomes necessary for AI Therapeutics or the Regulatory Authority to review any documentation relating to the study, the investigator must permit access to such records.

19.3. Data Recording/Case Report Forms

An eCRF will be completed for each subject enrolled into the clinical study. The investigator will review, approve, and sign/date each completed eCRF; the investigator's signature serves as attestation of the investigator's responsibility for ensuring that all clinical and laboratory data entered on the eCRF are complete, accurate, and authentic.

Source data are the clinical findings and observations, laboratory and test data, and other information contained in source documents. Source documents are the original records (and certified copies of original records) including, but not limited to, hospital medical records, physician or office charts, physician or nursing notes, subject diaries or evaluation checklists, pharmacy dispensing records, recorded data from automated instruments, x-rays, and so on. When applicable, information recorded on the eCRF shall match the source data recorded on the source documents.

Version 9, 18 Feb 2020

20. PUBLICATION POLICY

It is the intent of the sponsor to publish the complete study results in a timely manner that is appropriate to the project. Contribution to the project will be reflected in authorship. Separate publication of a portion of the study results (a sub-study) is discouraged.

Clinical Study Report
16.1 Study Information

Produced LANA 002A NIHL CLNO

Protocol: LAM-002A-NHL-CLN01

Version 9, 18 Feb 2020

21. STUDY DISCONTINUATION

Both the investigator and AI Therapeutics reserve the right to terminate the study at any time. Should this be necessary, both parties will arrange discontinuation procedures. The investigator will be responsible for notifying the relevant study center IRB. AI Therapeutics will be responsible for notifying the appropriate regulatory authorities. In terminating the study, the investigator and AI Therapeutics will assure that adequate consideration is given to the protection of the subjects' interests. As directed by AI, Therapeutics all study materials must be collected and all eCRFs completed to the greatest extent possible.

Protocol: LAM-002A-NHL-CLN01 Version 9, 18 Feb 2020

Appendix 1. Eastern Cooperative Oncology Group (ECOG) Performance Status Scale

Grade	Description
0	Fully active, able to carry on all pre-disease performance without restriction
1	Restricted in physically strenuous activity but ambulatory and able to carry out work of a light or sedentary nature, e.g., light house work, office work
2	Ambulatory and capable of all self-care but unable to carry out any work activities. Up and about more than 50% of waking hours
3	Capable of only limited self-care, confined to bed or chair more than 50% of waking hours
4	Completely disabled. Cannot carry on any self-care. Totally confined to bed or chair
5	Dead

Source: Oken 1982.

Version 9, 18 Feb 2020

Appendix 2. Criteria for Response Assessment

1. LYMPHOMA

1.1. Tumor Assessment Criteria

The determination of response and progression for subject with NHL will be based on standardized criteria (Cheson 2014).

1.2. Method of Assessment

Imaging-based evaluation will be used in this study as the primary basis of lymphoma assessment. CT scan is the preferred method for radiographic tumor assessment. Contrastenhanced scanning is preferred, but contrast material may be omitted in subjects for whom use of a contrast agent becomes medically contraindicated or if CT scanning is done in conjunction with PET. If available, PET scan data will be considered in response and progression assessment; however, PET scanning will not be a required component of assessment in this study. As necessary, bone marrow aspirate/biopsy (e.g., for confirmation of CR) or cytological/histological evaluation of lymph nodes, effusions, ascites, or other organ abnormalities) will be also be considered. Clinical palpation, chest x-ray, ultrasound, endoscopy, laparoscopy, radionuclide scan, or tumor markers will not be considered for response assessment. MRI scanning is not advised but may be used at the investigator's discretion in subjects for whom this becomes a necessary alternative to CT scanning.

For radiographic assessments, the same method of assessment and the same technique (e.g., scan type, scanner, subject position, dose of contrast, injection/scan interval) should be used to characterize each identified and reported lesion at baseline and during study treatment and follow-up. CT of the neck, chest, abdomen, and pelvis should be performed with cuts of ≤ 0.5 mm in slice thickness contiguously. If performed, whole-body FDG PET-CT scanning should be extended from the base of the skull to mid-thigh.

All relevant radiographic and clinical information required to make each tumor status assessment must be made available for source verification as requested by the study sponsor.

1.3. Timing of Assessments

During screening, clinical and imaging-based tumor assessments should be performed within the specified screening period. On-study tumor assessments should be performed as stipulated in Section 8.7. An end-of-therapy tumor assessment should be performed unless the subject already has radiographic confirmation of disease progression ≤ 4 weeks prior to study drug discontinuation. If a subject permanently discontinues treatment prior to objective documentation of lymphoma progression, investigators should ideally continue further follow-up of tumor status with assessments at ~ 12 -week intervals until disease progression is documented or until the initiation of a new post-study therapy for the subject's lymphoma.

Version 9, 18 Feb 2020

1.4. Identification and Follow-up of Tumor Lesions and Organomegaly

1.4.1. Index Lesions

Up to 6 lesions (e.g., lymph nodes, liver or spleen nodules, and/or other circumscribed extranodal masses) should be selected as index lesions that will be used to quantitate the status of the disease during study treatment. Ideally, the index lesions should be located in disparate regions of the body and include mediastinal, abdominal, and retroperitoneal areas of disease whenever these sites are involved. For subjects with FDG-avid lymphomas undergoing PET, selection of FDG-avid lesions is preferred.

Index lesions will be measured and recorded at baseline and at the stipulated intervals during treatment. The largest cross-sectional dimensions (i.e., the LD × LPD will be recorded (in cm) for each index lesion. Using the LD and LPD, the product of the perpendicular diameters (PPD) for each index lesion will be calculated. The PPDs and the SPDs for all index lesions will be calculated and recorded. The baseline and nadir PPDs of individual lesions and the baseline and nadir SPDs will be used as references by which objective tumor response and progression will be characterized during treatment. All PPD and SPD measurements will be reported in centimeters squared.

1.4.2. Nodal Index Lesions

A nodal mass may be selected as a nodal index lesion if it is both abnormal and measurable at baseline. A lymph node lesion is considered abnormal if it has a single diameter that is > 1.0 cm and is considered measurable if it has 2 perpendicular diameters that can be accurately measured in cross section with the LD being ≥ 1.0 cm and the LPD also being ≥ 1.0 cm.

Abnormal, measurable nodal lesions will be subcategorized as either large or small.

- Large nodal lesions have an LD that is > 1.5 cm and an LPD that is ≥ 1.0 cm.
- Small nodal lesions have an LD that is > 1.0 cm and ≤ 1.5 cm and an LPD that is > 1.0 cm.

Index lesions measuring > 1.5 cm in the LD, regardless of the measurement of the LPD, will be prioritized during baseline index lesion selection.

At follow-up timepoints, the PPDs for individual nodal lesions and the SPD of all nodal index lesions will be considered. Because nodal index lesions that have one or both diameters > 0 cm and < 1.0 cm cannot be reliably measured, a default value of 1.0 cm will be assigned for each diameter that meets these criteria and the resulting PPD will be used in SPD calculations. Based on this convention, a CR may be achieved even if an SPD value is > 0 cm² (i.e., if all lymph nodes measure < 1.0 cm²).

New or enlarging nodal lesions that are still ≤ 1.0 cm by ≤ 1.0 cm will not be considered to represent recurrent or PD. A new node that measures > 1.5 cm in any diameter or a new node that measures > 1.0 cm to ≤ 1.5 cm in the LD and measures > 1.0 cm in the LPD will be considered PD.

In cases in which a large lymph node mass has split into multiple components, only those elements that are > 1.0 cm in ≥ 1 diameter will be considered abnormal and used in calculating

Version 9, 18 Feb 2020

the SPD. Components that are ≤ 1.0 cm in the LD are assumed to be normal lymph node structures. PD will not be based on the growth of a lesion sub-component until it meets the criteria for abnormal. Lesion sub-components that are abnormal (> 1.0 cm in \geq 1 diameter) will have the true PPDs calculated with the result used only for calculating an accurate nadir. Lesion subcomponents that are normal (\leq 1.0 cm in the LD) will have the default PPD of 1.0 cm² (1.0 cm x 1.0 cm) stored only for the purposes of calculating the nadir value.

If lesions merge, a boundary between the lesions will be established so the LD of each individual lesion can continue to be measured. If the lesions have merged in a way that they can no longer be separated by this boundary, the newly merged lesion will be measured bidimensionally.

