1.5.2. Partial Response

To satisfy criteria for PR, all of the following conditions must be attained:

- No evidence of new disease
- A \geq 50% decrease from baseline in the SPD of the index nodal and extranodal lesions
- No increase from the nadir in the size of non-index disease
- No increase from the nadir in the size of the liver or spleen and no new liver or spleen enlargement
- If PET performed:
 - Typically FDG-avid lymphoma: if no baseline PET scan or if the PET scan was positive before therapy, the on-treatment PET is positive in ≥ 1 previously involved site– i.e., score of 4 (uptake moderately > liver) or score of 5 (uptake markedly > liver) on the Deauville 5-point scale but with reduced uptake compared with baseline. If baseline PET was performed and was negative, there is no new PET evidence of disease.
 - Variably FDG-avid lymphoma/FDG-avidity unknown: if no pretreatment PET scan or if the pretreatment PET scan was negative for lymphoma, CT criteria should be used in assessing the tumor during treatment. If the PET scan was positive before therapy, the on-treatment PET is positive in ≥ 1 previously involved site.
- Persistence of bone marrow involvement in a subject who meets other criteria for CR based on the disappearance of all nodal and extranodal masses

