In cases in which a large lymph node mass has split into multiple components, only those elements that are > 1.0 cm in ≥ 1 diameter will be considered abnormal and used in calculating the SPD. Progression of the lesion can only be based on the SPD of abnormal sub-components. Lesion sub-components that are considered normal but measurable will have the true PPDs calculated, with the result used only for calculating an accurate nadir. Similarly, lesion sub-components that are visible but neither abnormal nor measurable will have the default PPD of 1.0 cm^2 ($1.0 \text{ cm} \times 1.0 \text{ cm}$) stored only for the purposes of calculating the nadir SPD value.

If lesions merge, a boundary between the lesions will be established so the LD of each individual lesion can continue to be measured. If the lesions have merged in a way that they can no longer be separated by this boundary, the newly merged lesion will be measured bi-dimensionally.

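### Appendix 2 gives conflicting rules for the fragments of a split nodal mass, so one scan can be read as SD or as meeting the PR size criterion, and SPD-based progression can be called late

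*Combined protocol and SAP*

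**What the plan says.** Appendix 2, 1.4.2 (NHL) makes four statements that bear on a nodal mass that has split.

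- Abnormal fragments count: "only those elements that are > 1.0 cm in ≥ 1 diameter will be considered abnormal and used in calculating" the SPD.
- Abnormal fragments, defined by the same size test, "will have the true PPDs calculated with the result used only for calculating an accurate nadir".
- Normal fragments (longest dimension at most 1.0 cm) get a default product (PPD) of 1.0 cm², "stored only for the purposes of calculating the nadir value".
- For nodal index lesions in general, a diameter too small to measure is set to 1.0 cm "and the resulting PPD will be used in SPD calculations".

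The CLL/SLL text in 2.4.1 also puts abnormal fragments in the SPD, but attaches the nadir-only wording to a different group: "Lesion sub-components that are considered normal but measurable will have the true PPDs calculated, with the result used only for calculating an accurate nadir". Its default for smaller fragments is kept for the nadir SPD, named as such.

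On use of these values, 1.4.1 states: "The baseline and nadir PPDs of individual lesions and the baseline and nadir SPDs will be used as references". PR requires at least a 50% "decrease from baseline in the SPD of the index nodal and extranodal lesions" (1.5.2). Progression on the SPD requires a rise of at least 50% from nadir (1.5.4), and 1.5 defines the nadir as the smallest measurement recorded.

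**The concern.** There are two separate problems.

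**Response.** The word 'only' in the second statement takes abnormal fragments out of the current SPD, where the first statement has just put them. Response is investigator-assessed (5.5), so two sites could follow different sentences and score the same scan differently. The response rate and the FL accrual boundaries in 14.1.2 count individual responders.

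**Progression.** If normal fragments add to the nadir SPD but not to the SPD compared with it, the two sums are built from different fragments. The nadir is then too high for the comparison, and progression by SPD is called later or not at all. Duration of response and PFS (14.9) depend on that date.

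**Working it through.** The plan gives no figure to reproduce, so the rules are applied directly. Lesion sizes are illustrative assumptions. PPD = longest dimension (LD) × longest perpendicular dimension (LPD); SPD = sum of PPDs.

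**1. PR or SD.** Baseline is one index mass, 6.0 × 5.0 = 30 cm². It splits into three pieces of 3.0 × 2.5 = 7.5 cm².
- First sentence: SPD = 3 × 7.5 = 22.5; change = 22.5/30 − 1 = −25%. This is SD.
- Later sentence: SPD = 0; change = −100%. The PR size criterion is met.

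Other index lesions dilute the contrast but need not remove it. Take a 4.0 × 3.0 = 12.0 cm² mass splitting into 2.5 × 2.0 and 2.0 × 1.5 (8.0 cm²), with an unchanged second lesion of 6.0 cm². Baseline is 18.0. The first sentence gives 14.0 (−22%, SD); the later one gives 6.0 (−67%, PR size criterion met).

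**2. SPD-based PD.** Let S be the SPD of abnormal fragments at best response, k the number of normal fragments at 1.0 cm² each, and S′ the later SPD of abnormal fragments, with the normal fragments staying normal. PD is reached when:
- normal fragments are omitted from both sums: S′ ≥ 1.5S
- defaults are included in both sums: S′ + k ≥ 1.5(S + k), so S′ ≥ 1.5S + 0.5k
- as written, if the stored value belongs to the nadir SPD: S′ ≥ 1.5(S + k)

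The last threshold exceeds the first by 1.5k cm² and the second by k cm². With k = 0 there is no delay; the shift is never toward earlier PD.

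**3. Does the individual-node rule in 1.5.4 make this harmless in NHL?** For one larger fragment, largely yes. Take one 2.0 × 2.0 cm piece (4.0 cm²) with three normal fragments. The as-written SPD threshold is 1.5 × 7.0 = 10.5 cm². The node rule fires earlier: it needs a PPD rise of at least 50%, LD above 1.5 cm, a change of at least 0.5 cm in one diameter, and a dimension of at least 2.0 cm. The largest PPD that can escape it is just under 2.5 × 2.5 = 6.25 cm² (6.25/4.0 − 1 = +56%).

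For diffuse growth, no. Take three 1.5 × 1.2 cm pieces (S = 3 × 1.8 = 5.4) with one normal fragment (k = 1). Each piece grows to 1.9 × 1.55 cm.
- S′ = 3 × 2.945 = 8.84 cm² (8.84/5.4 − 1 = +64%).
- Per node, LD rises 0.4 cm (27%) and LPD 0.35 cm (29%), and no dimension reaches 2.0 cm. No individual-node criterion is met.
- Thresholds: 1.5 × 5.4 = 8.1 (omitted from both); 8.1 + 0.5 = 8.6 (included in both); 1.5 × 6.4 = 9.6 (as written).

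The scan is PD under either consistent rule and not PD as written.

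**4. Sensitivity of the FL boundary.** For monotherapy, 8/20 is on the list in 14.1.2 and has an exact one-sided 95% lower bound of 21.7%. With one of those responses read as SD, 7/20 has 17.7%, below the required 20%.

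**The case against.** The strongest reply is that no sensible reader would score three 3.0 × 2.5 cm pieces as zero, because that would empty the first sentence of meaning. Most investigators would probably follow the first sentence. But the later sentence says 'only', names fragments by the same size test, and sits in the same paragraph. Nothing in the part of the document available for this review says which governs.

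On progression, 1.4.2 speaks of a nadir value, while only 2.4.1 says nadir SPD. Section 1.4.1 uses both lesion-level and SPD nadirs, and 1.5 takes the smallest measurement recorded. If 1.4.2 means the fragment's own nadir, the SPD delay in NHL disappears once abnormal fragments are counted. That stands: the NHL mismatch is a plausible reading, not an explicit one.

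Three stronger conclusions may tempt a reader, and the documents do not support them.

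- *That 2.4.1 proves the NHL sentence names the wrong group.* In 1.4.2 a node is abnormal above 1.0 cm and measurable from 1.0 × 1.0 cm, so a normal but measurable node could only be exactly 1.0 × 1.0 cm. In 2.4.1 the general cut-off for an abnormal node is 1.5 cm. The difference in wording need not be a copying slip.
- *That PD in NHL needs a rise of about 163% (10.5/4.0 = 2.625).* That follows from the SPD rule alone. Section 1.4.2 bars PD on a fragment's growth only until it is abnormal, which implies that the individual-node rule applies afterwards, and that rule fires long before 10.5 cm².
- *That CLL/SLL is more exposed.* Section 2.4.1 does restrict lesion progression to the SPD of abnormal fragments, but 2.5.4 separately makes a 50% rise in the LD of an individual node PD. No expansion cohort enrols CLL/SLL (6.1.2).

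It is also fair that DLT frequency is the primary endpoint (5.4) and response is secondary.

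**Conclusion.** The contradiction over abnormal fragments in 1.4.2 is literal and should be corrected. For a mass that is the only index lesion, one scan can be −25% or −100%. The second figure meets only the PR size criterion; the other PR conditions still apply.

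The nadir mismatch for normal fragments is explicit in 2.4.1 and conditional in 1.4.2. It needs at least one normal fragment that stays normal. In NHL it matters mainly when several fragments grow together without any one of them meeting the individual-node rule.

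The documents do not say how often masses split, so no size can be put on the effect on ORR, duration of response or PFS. The 8/20 against 7/20 comparison shows only that one reclassified response can decide the FL boundary, not that this is likely.

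**What to change.** 1. **Section 1.4.2, abnormal fragments.** Delete 'only' from the nadir sentence and state that the true PPDs of abnormal fragments enter both the current SPD and the nadir SPD. Importing the normal-but-measurable wording from 2.4.1 would not work: it would create an almost empty class that overlaps the next sentence.

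2. **Sections 1.4.2 and 2.4.1, normal fragments.** Choose one convention and apply it identically to the current SPD and the nadir SPD. One option is the 1.0 cm² default in both, which matches the general default rule in 1.4.2. It also guards against false PD. With S = 3.0 and two normal fragments growing to 1.1 × 1.1 cm, the SPD becomes 3.0 + 2 × 1.21 = 5.42. That is +8% against a nadir of 5.0 with defaults, but +81% against 3.0 without.

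3. **Consequential edits.** Bring the first split-mass sentence and the stored-only-for-the-nadir wording into line with that choice in both sections, and say nadir SPD in 1.4.2 if that is meant. In 2.4.1, reconcile the sentence limiting lesion progression to abnormal fragments with the individual-LD rule in 2.5.4.

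The choice in item 2 also affects PR. From a 12.0 cm² baseline, a 5.0 cm² abnormal fragment with two normal ones is −58% if the normal ones are omitted and −42% if they carry the default (7.0/12.0). It should therefore be fixed without reference to the response data.

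The cost is a few edited sentences in Appendix 2. No new data or assessments are needed; any split masses already scored should be re-read under the chosen rule.
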